## **5.4 RANDOMIZATION**

### **5.4.1 Method of Assigning Patients to Treatment Groups**

The trial will be conducted in a double-blind, placebo-controlled manner. Allocation to 1 of 2 treatment arms will occur on a 1:1 ratio within each sites with a block of size 4 based on a predefined randomization code generated by the TREAT data coordinating unit (DCU).

The investigator or designee will be required to register the patient on the OnCore system (TREAT's data management system) and will provide patient data to properly randomize and allocate the patient to treatment. A randomization number will be assigned and study medication dispensing information (e.g., bottle number(s)) will be provided.

### **5.4.2 Site Numbers**

Each trial site selected to participate in this trial will be assigned a Site Number by the TREAT consortium. The Site Number will be used to categorize patient data and to identify the site and or investigator within trial documents.

### **5.4.3 Screening Numbers**

At the Screening Visit, after the patient has provided written informed consent, the patient will be assigned a unique 5 digit subject ID number.

### **5.4.4 Randomization Numbers and Schedule**

Subjects will be randomized to one of two treatment groups with stratification by site and block of size 4. Random assignment will be generated by the coordinating unit and provided to the site pharmacist for randomized packing for maintenance of blinding.

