### Planned Number of Investigational Sites

Four investigational trial sites at Indiana University in Indianapolis, Mayo Clinic in Rochester, Virginia Commonwealth University in Richmond, and Einstein Medical Center in Philadelphia

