### Planned Number of Patients

Approximately 60 patients (30 patients per arm) will be randomized in a 1:1 ratio to 1 of 2 treatment arms: **(a)** placebo, or **(b)** 10 mg OCA.

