#### 1.4 SUMMARY OF KNOWN POTENTIAL RISKS WITH STUDY MEDICATION

Pruritus has been observed in the multiple dose trials of OCA in primary biliary cirrhosis (PBC) and was the most common AE seen in the PBC 747-202 Trial, DB phase, with 67% of patients reporting a treatment emergent AE (TEAE) of pruritus. There was a relationship between the dose of OCA administered and the incidence (at 25 mg and 50 mg only), severity, and the timing of the onset of pruritus, which occurred almost invariably within the first 14 days of treatment at 50 mg. Pruritus was least tolerated at 50 mg with 24% of patients discontinuing at this dose due to pruritus.

In the 747-201 Trial, DB phase, pruritus was the most common AE that occurred in any treatment group, 50 mg (94%) and 10 mg (70%), and at a rate higher than in the placebo (30%) group. Similarly, pruritus has been the most commonly reported AE in the 747-201 LTSE to date. The severity of pruritus shows an apparent improvement with increasing dose of OCA in the LTSE. This suggests that patients who do not develop severe pruritus at lower doses are likely to tolerate higher doses if titrated up.

The mechanism of pruritus in cholestatic liver disease is unknown. Recently, autotaxins and lysophosphatidic acid have been implicated in pruritus of cholestasis [Kremer 2009, 2010, 2011]. Recent data [Kremer 2011] suggest that autotaxins may be increased in patients with the worst pruritus taking 50 mg in the 747-202 trial and that patients with high autotaxin levels were more likely to develop severe pruritus. However, plasma autotaxin levels did not explain the pruritus in the majority of patients. Assays of the plasma from the subjects receiving 250 mg dose in the multiple dose normal volunteers trial (747-102) did not show a difference in autotaxin levels between the pruritic and non-pruritic subjects. Bile acid concentrations in the PBC trial 747-202 have not shown an association with pruritus.

In the PBC 747-202 Trial, DB phase, besides pruritus, only nausea (mild or moderate) was seen more frequently in all 3 OCA groups than in the placebo group. In the 747-201 DB phase, only urinary tract infection was seen more frequently in both OCA groups than the placebo group. The current IB outlines other AEs observed in association with the use of OCA.

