### **5.3.2 Blinding**

All study medication will be visually identical for the OCA and placebo treatment arms, thus ensuring the double-blind nature of the trial. Study medication bottles will not be labeled with either a patient randomization number or tablet strength, to ensure that neither patient nor investigator is unblinded.

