## **5.5 UNBLINDING PROCEDURES**

### **5.5.1 Unscheduled, Emergency Unblinding**

The site pharmacist will be unblinded to randomization codes and corresponding treatment assignment as s/he will overlabel each bottle to apply the blind, prior to dispensing to any subjects at the site. Additionally, the randomization codes and corresponding treatment assignment will be maintained by the TREAT DCU. The study designated physician ([name] or his designee), or the individual investigators will not have access to this information. In the event that a medical emergency necessitates unblinding (i.e., in situations where knowledge of the blinded treatment is necessary for further medical management of the patient), the site investigator (or his/her designee) will contact the designated study physician to discuss the rationale for unblinding. If there is a difference of opinion between the designated study physician and the site investigator, then the site investigator retains the final right to seek unblinding. The designated study physician will

communicate with the DCU about the decision to unblind the subject and then the DCU will unblind the subject by interacting directly with the site investigator.

The Data and Safety Monitoring Committee (DSMC) will be able to unblind patients. Cases of premature unblinding (as noted above) will be reviewed by the DSMC.

Access to randomization codes and corresponding treatment assignment will also be made available to the designated study physician who is responsible for reporting SAEs and suspected unexpected serious adverse reactions (SUSARs) to the Regulatory Authorities and should be accessed only in the event that reporting necessitates unblinding. Aside from the site pharmacist who conducts the drug overlabeling, no other site personnel will have direct access to blinded patient treatment codes until all trial data have been entered onto the trial database and validated, and the database locked.

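### The protocol prints a fixed block of 4 within site: if earlier allocations leak, one third of assignments become certain, and mixed, undisclosed block sizes would modestly reduce (not remove) that predictability

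*Combined protocol and SAP*

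**What the plan says.** Randomization is 1:1, stratified by site. Section 5.4.4 gives the scheme: "Subjects will be randomized to one of two treatment groups with stratification by site and block of size 4". The Methodology part of the synopsis uses the same wording, and section 5.4.1 specifies a "1:1 ratio within each sites with a block of size 4 based on a predefined randomization code". No varying sizes are mentioned, and the block size is not reserved to a separate document.

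The synopsis plans four sites and about 60 patients, 30 per arm. Sections 4.1 and 8.3 still say three sites.

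The protocol also sets safeguards:

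- Section 5.3.2: "All study medication will be visually identical for the OCA and placebo treatment arms". Bottles carry no randomization number.
- Section 5.2.1: bottle numbers are non-sequential and say nothing about content.
- Section 5.5.1: codes sit with the DCU and the site pharmacist, and investigators do not have access to them.

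Section 5.5.1 also describes how an allocation can become known. The site pharmacist is unblinded. After an emergency request, "the DCU will unblind the subject by interacting directly with the site investigator". The Data and Safety Monitoring Committee (DSMC) can unblind patients, and the designated study physician can obtain codes when regulatory reporting requires it.

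**The concern.** Investigators register each patient themselves (section 5.4.1), so they know the order of enrolment at their site. With a fixed, printed block size they can count where each block starts and ends. Any allocation they learn then carries information about the next patient in that block. An investigator who can predict the next assignment can influence who is enrolled next, or when. Adjusting for baseline MELD (section 10.1) would not fully correct selection on prognosis that MELD does not capture, such as the likelihood of abstinence.

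Side effects could be a further clue. Section 1.4 reports pruritus in one trial in primary biliary cirrhosis (PBC) as "50 mg (94%) and 10 mg (70%), and at a rate higher than in the placebo (30%) group".

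**Working it through.** **1. The plan's own figure.** Section 10.2 gives 80% power for 0.78 SD with 27 patients per arm. 30 × 0.9 = 27. An exact two-sample t-test with n = 27 per arm, d = 0.78 and two-sided alpha 0.05 (assumed; the plan states none) gives 80.3%. The smallest detectable effect is 0.777. The figure reproduces and does not depend on block size.

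**2. Fixed block of 4, all earlier allocations in the block known.** There are 4!/(2!·2!) = 6 equally likely sequences.

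- Certain assignments by position: 0, 0, 1/3 (when the first two match), 1. Mean = (0 + 0 + 1/3 + 1)/4 = 33.3%.
- Best-guess accuracy by position: 1/2, 2/3, 1/3 + (2/3)(1/2) = 2/3, 1. Mean = (1/2 + 2/3 + 2/3 + 1)/4 = 70.8%.

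**3. Randomly mixed sizes.** This was simulated with an optimal guesser who knows all earlier allocations and the set of possible sizes, each size equally likely. A list of 15 assumes equal enrolment, 60/4 = 15 per site.

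| Sizes | Certain, list of 60 | Best guess, list of 60 | Certain, list of 15 | Best guess, list of 15 |
|---|---|---|---|---|
| Fixed 4 | 33.3% | 70.8% | 28.9% | 68.9% |
| 4 and 6 | 5.5% | 69.1% | 5.9% | 67.6% |
| 2, 4 and 6 | 4.0% | 70.1% | 3.6% | 68.5% |
| 2 and 4 | 10.9% | 72.1% | 10.1% | 70.6% |

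The certain share falls sharply. Best-guess accuracy barely moves, and sizes 2 and 4 make it slightly worse.

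**4. One unblinded patient.** In a block of n, the next patient in the same block is on the other arm with probability (n/2)/(n − 1): 2/3 for n = 4 and 3/5 for n = 6.

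- Fixed 4, next patient in the same block: 66.7%. The investigator can tell when this applies.
- Sizes 4 and 6, over adjacent pairs within a block: (3 × 2/3 + 5 × 3/5)/8 = 5/8 = 62.5%.
- Sizes 4 and 6, when the investigator cannot tell whether the block has ended, over all positions: [0.5(3 × 2/3 + 0.5) + 0.5(5 × 3/5 + 0.5)]/5 = 60%. The same average for fixed 4 is (3 × 2/3 + 0.5)/4 = 62.5%.

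Like for like, the gain is about 4 points within a block and 2.5 points over all positions.

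**5. Guessing from pruritus only, fixed 4.** With 70% v 30%, the second patient is guessed correctly with probability 0.7 × 2/3 + 0.3 × 1/3 = 56.7%. Enumeration over the four positions gives 50.0, 56.7, 56.7 and 61.6%, mean 56%. With an assumed 70% v 50% the mean is 53%; with no difference it is 50%. Under sizes 4 and 6 the 56% becomes about 55%.

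**6. Cost in balance.** The largest imbalance inside a block rises from 2 (half of 4) to 3 (half of 6). With four sites of 15, the mean absolute arm difference is 1.5 with fixed 4 and 1.6 with sizes 4 and 6. The largest difference in 20,000 simulated trials is 4 and 8 respectively. A difference of 8 among 54 evaluable patients (31 v 23) gives 79.4% power against 80.3%, a loss of 0.9 points.

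**The case against.** The strongest reply is that a fixed small block is a defensible choice in a double-blind trial with restricted codes, and that nothing in the documents shows a leak. Most of this stands. The one-third figure needs every earlier allocation in the block, so two or three patients in the same site's block, while enrolment is still open. A single emergency unblinding makes nothing certain. Such unblinding is limited to medical emergencies, is discussed with the designated study physician, and is reviewed by the DSMC. If a pharmacist disclosed the forward list rather than past allocations, no block scheme would help.

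The pruritus evidence is also weak. Section 1.2.2.1 reports that in the other PBC trial incidence was not raised at 10 mg, the dose used here, and no rate in alcoholic hepatitis is given. The 56% is therefore the top of a range that starts at chance. Eligibility is rechecked on Day 0 against a MELD window and a recent-drinking criterion, which limits how far an investigator could time entry within the 8-week screening period.

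What does not fall away is that the block size is printed in three places, the documents give no reason for printing it, and withholding it costs little.

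A reader might infer that varying undisclosed sizes would abolish predictability for free. They would not: above-chance guessing comes from balancing within small blocks and persists at about 69%.

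**Conclusion.** The point holds as a minor design improvement. Disclosing a fixed block of 4 within site means that, if earlier allocations become known, one third of assignments are certain. Undisclosed sizes of 4 and 6 cut this to about 6%. Best-guess accuracy changes only from about 71% to 69%, and the next allocation after one unblinding from 67% to about 60-63%.

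A reader might also infer that allocation in this trial is predictable, or that selection bias is present. The documents do not support that. Tablets are identical, investigators have no access to codes, and pruritus alone allows about 50-56% correct guesses.

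Assumptions: two-sided alpha 0.05, equal probability of each block size, equal enrolment of 15 per site for the balance figures, and PBC pruritus rates as the upper case.

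**What to change.** - At the next amendment, delete the block size from the synopsis (Methodology, Randomization) and from sections 5.4.1 and 5.4.4. State only that lists are stratified by site with permuted blocks, and that the details are held in a restricted DCU file.
- For any list not yet issued, have the DCU generate randomly varying sizes, for example 4 and 6. Sizes 2 and 4 should not be used, since they do not lower best-guess accuracy.
- Leave issued lists in place. Assignments go to site pharmacists, who overlabel bottles before dispensing, so replacement could mean relabelling stock and switching in mid-block. The documents do not show that to be cheap.
- For issued lists, whose block size is already known, report each unblinding with its position in the block.

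The cost is DCU time for any new list, a text amendment reviewed by each IRB (section 11.2), and a possible within-block imbalance of 3 instead of 2, worth less than 1 point of power. The documents do not say which lists, if any, remain unissued, so the benefit may be confined to a later site or a list extension.

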## **5.5 UNBLINDING PROCEDURES**

### **5.5.1 Unscheduled, Emergency Unblinding**

The site pharmacist will be unblinded to randomization codes and corresponding treatment assignment as s/he will overlabel each bottle to apply the blind, prior to dispensing to any subjects at the site. Additionally, the randomization codes and corresponding treatment assignment will be maintained by the TREAT DCU. The study designated physician ([name] or his designee), or the individual investigators will not have access to this information. In the event that a medical emergency necessitates unblinding (i.e., in situations where knowledge of the blinded treatment is necessary for further medical management of the patient), the site investigator (or his/her designee) will contact the designated study physician to discuss the rationale for unblinding. If there is a difference of opinion between the designated study physician and the site investigator, then the site investigator retains the final right to seek unblinding. The designated study physician will

communicate with the DCU about the decision to unblind the subject and then the DCU will unblind the subject by interacting directly with the site investigator.

The Data and Safety Monitoring Committee (DSMC) will be able to unblind patients. Cases of premature unblinding (as noted above) will be reviewed by the DSMC.

Access to randomization codes and corresponding treatment assignment will also be made available to the designated study physician who is responsible for reporting SAEs and suspected unexpected serious adverse reactions (SUSARs) to the Regulatory Authorities and should be accessed only in the event that reporting necessitates unblinding. Aside from the site pharmacist who conducts the drug overlabeling, no other site personnel will have direct access to blinded patient treatment codes until all trial data have been entered onto the trial database and validated, and the database locked.

#### **5.6 PRIOR AND CONCOMITANT MEDICATIONS OR PROCEDURES**

Relevant information about all concomitant drugs (including prescribed, over the counter, or herbal preparations) taken prior to and during the trial must be recorded in the source documents and CRF, as well as any dose or dose regimen changes that occur during the trial.

#### **5.7 TREATMENT COMPLIANCE**

The investigator should assess the patient's compliance with dosing of study medication on an ongoing basis, at least at each visit, and confirm by conducting drug accountability (i.e., count of returned tablets).

Patients should be instructed to retain all bottles of study medication, even if empty, and to return them to the investigator at the subsequent visit. The investigator or designee should perform drug accountability and, if applicable, follow up with the patient to retrieve any study medication that has not been returned.

If the investigator has concerns about a patient's dosing compliance s/he should discuss this with the patient, assess the reasons for noncompliance and the likelihood that the patient will remain noncompliant, and notify the designated study physician accordingly. Continued trial eligibility should be assessed based on the patient's compliance with study medication dosing and clinic visits.

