Highly statistically ( $p < 0.0001$ ) and clinically significant reductions in ALP from DB baseline were seen with OCA from 3 months through 1 year.

**Protocol 747-201**, a monotherapy trial comparing the effects of 10 mg and 50 mg OCA versus placebo, is ongoing in the LTSE phase (Protocol 747-201). The following was observed in the DB phase of this trial (32):

Highly statistically and clinically significant relative and absolute reductions in ALP were seen with both doses (10 and 50 mg) of OCA versus placebo ( $p < 0.0001$ ) showing it has substantial efficacy in PBC when given as monotherapy.

Statistically significant improvements were also seen in GGT and in conjugated bilirubin with both doses. ALT and AST changes were not statistically significant though decreased by approximately 35% and 20%, respectively.

Statistically significant changes were seen in several domains of the PBC-40 questionnaire.

Statistically significant reductions were seen in C-reactive protein and IgM.

Safety: As in the 747-202 PBC trial, pruritus was the most common AE. The incidence of pruritus in the OCA groups, 50 mg (94%) and 10 mg (70%), was higher than in the placebo (30%) group. Similarly, the severity of pruritus increased with the dose of OCA. This translated into a higher discontinuation rate for the treated patients, notably in the 50 mg group of which 38% discontinued due to pruritus.

This trial is ongoing in the open label LTSE phase. Additional details regarding the phase 2 PBC trials and current updates about the LTSE phases are provided in the current IB.

**Protocol 747-301**, a phase 3, double-blind, placebo-controlled, parallel-group trial of OCA in patients with PBC is currently ongoing. This phase 3 trial has been designed to assess the efficacy, safety and tolerability of lower doses (5 mg and 10 mg) of OCA in patients with PBC. The primary endpoints are ALP and total bilirubin, assessed together as a composite endpoint, and safety.

Participating subjects are either continuing their pre-trial dose of UDCA or are not treated with UDCA, if they were unable to tolerate it previously. A five-year LTSE phase is planned to follow the initial 12 month DB phase of the trial. Enrollment has been completed and 217 patients have been randomized in a 1:1:1 ratio to (a) placebo, (b) 10 mg OCA, or (c) 5 mg titrating to 10 mg OCA. During the open label LTSE phase, patients may receive up to 25 mg of OCA for up to 5 years and continue their pre-trial dose of UDCA.

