### **4.3 PATIENT WITHDRAWAL FROM THE TRIAL**

#### **4.3.1 Reasons for Mandatory Trial Discontinuation**

If a female patient becomes pregnant, she must stop taking study medication and must be withdrawn from the trial. The patient must be followed by the investigator through the end of her pregnancy. The mother (and infant) will be followed as considered appropriate by the investigator and the study designated physician ([name] or his designee). For reporting purposes, pregnancy is not considered a serious adverse event (SAE).

During the trial, if Maddrey's Discriminant Factor (DF) increases by 5 points and also exceeds 32, or MELD scores increases by 5 points and also exceeds 20, the study

medication should be stopped, however the participant will remain in the trial, completing procedures as detailed in the Schedule of Procedures (Table 1). Treating physicians may offer any other treatment that is considered as medically indicated and appropriate.

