#### **4.3.2 Other Reasons for Trial or Treatment Discontinuation**

The following events are considered appropriate reasons for a patient to discontinue from the trial:

- The patient withdraws consent or requests to be withdrawn from the trial. It is fully understood that all patients volunteer for the trial and that they may withdraw their consent at any time.
- The patient experiences an adverse event that in the opinion of the site investigator or the primary investigator of the trial (i.e., study designated physician, [name]) is caused by or exacerbated by any of the trial procedures or study medication, of sufficient intensity to warrant discontinuation.
- The patient refuses to comply with the requirements for trial participation.

When possible, the investigator should discuss the potential discontinuation of a patient with the study designated physician ([name] or his designee) in advance.

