## 10. STATISTICAL METHODS

### 10.1. ANALYSIS SETS

Primary end point: Analysis will be based on intention-to-treat principle. We will evaluate the main outcome, change in MELD score at day 42, in the framework of the repeated measurements analysis of covariance (ANCOVA) model. Specifically, MELD score at each follow-up visit will be used as the outcome variable. The main predictor is treatment group (GROUP). We will adjust for time (visit) and baseline MELD score and include the interaction between GROUP and visit. The interaction term allows evaluation of GROUP difference at each visit. The main comparison is the differences of MELD score change at day # 28 between two groups. A random intercept will be used to adjust for the correlation among the observations from the same subject. We will also evaluate the GROUP difference at 90 and 180 days in the framework of above repeated ANCOVA model.

SAEs during treatment: The primary analysis is to compare the proportion of patients having at least one SAE during the treatment period between the two groups using Chi-square tests. *SAE during follow-up* will be analyzed similarly. Other safety outcomes include AEs, discontinuations, pre-defined laboratory abnormalities, and predefined EKG abnormalities. Other continuous outcomes will be analyzed in a similar way to MELD score, binary outcomes will be analyzed in a similar way to SAE, and censored time-to-event outcomes will be analyzed using appropriate survival analysis tools (e.g., Kaplan-Meier plots, Cox models).

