#### **10.5. HANDLING OF MISSING DATA**

Missing values will not be imputed and only observed values will be used in data analyses and presentations.

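### Sections 5.7 and 4.3.2 permit randomised patients to leave the trial for non-compliance or drug-related adverse events, with no guarantee of follow-up to the scheduled visits

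*Combined protocol and SAP*

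**What the plan says.** Section 5.7 (Treatment compliance), after describing tablet counts and how to handle poor compliance, ends: "Continued trial eligibility should be assessed based on the patient's compliance with study medication dosing and clinic visits". It gives no threshold and no consequence, and it refers to the trial, not to study medication.

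The heading of section 4.3.2 covers trial or treatment discontinuation, but its opening sentence names only the trial: "The following events are considered appropriate reasons for a patient to discontinue from the trial". Besides withdrawal of consent, the list includes an adverse event that "is caused by or exacerbated by any of the trial procedures or study medication, of sufficient intensity to warrant discontinuation" and the case where "The patient refuses to comply with the requirements for trial participation".

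Three other sections bear on follow-up:

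- 4.3.1: when the discriminant function or MELD score worsens past the stated trigger, study "medication should be stopped, however the participant will remain in the trial".
- 4.3.3: a patient who is off drug but still in the study keeps the Table 1 schedule, and visits are not brought forward.
- 6.2.9: patients who withdraw consent or stop treatment early in the treatment phase are asked for the Day 42 assessments; those who leave during follow-up are asked for the Day 180 assessments.

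On analysis, 10.1 states "Analysis will be based on intention-to-treat principle". Section 10.5 (Handling of missing data) states "Missing values will not be imputed and only observed values will be used in data analyses and presentations". No sensitivity analysis for missing data is described.

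**The concern.** Compliance and drug-related adverse events arise after randomisation, and treatment can influence both. If either can end a patient's participation, the patients who remain under observation are no longer exactly the groups that were randomised. Both primary outcomes are exposed: MELD change at 6 weeks, and the proportion of patients with at least one SAE during treatment.

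The protocol gives some reason to think that loss could differ by arm. In study 747-201, pruritus incidence on OCA, at "50 mg (94%) and 10 mg (70%), was higher than in the placebo (30%) group". Information lost because follow-up stopped cannot be recovered at the analysis stage.

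**Working it through.** **1. Does any section guarantee follow-up after removal under 5.7 or 4.3.2?**

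- 4.3.1 keeps the patient in the trial, but only for the discriminant function/MELD trigger.
- 4.3.3 continues the schedule, but only for a patient who is still in the study. It does not say who stays.
- 6.2.9 yields an assessment with Day 42 content. As an early-termination procedure it gives an exit value, not a scheduled week-6 value, and it cannot capture a first SAE that occurs afterwards.
- 8.1 and 9.1.1 tie the end of adverse event recording to completion of trial participation (Day 180). They do not say what happens when participation ends sooner.
- 9.4 extends follow-up of certain events still ongoing at the final visit. It does not cover new events.

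So no section requires scheduled MELD values or SAE collection for a removed patient through Days 42, 90 and 180. Sections 4.3.3 and 6.2.9 also pull in different directions for a patient who stops drug but stays in: one keeps the schedule, the other calls for early-termination assessments.

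**2. The plan's own power figure.** Section 10.2 gives 30 per arm, 10% dropout at day 28, a two-sample t-test and an effect size of 0.78 SD. Alpha is not stated; 0.05 two-sided is assumed.

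- Evaluable per arm: 30 × 0.90 = 27.
- Standard error of the difference: √(2/27) = 0.272 SD.
- Noncentrality: 0.78 / 0.272 = 2.87, with 52 degrees of freedom.
- Power: 80.3%, so the stated 80% reproduces. The smallest detectable effect is 0.777 SD.

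**3. Power if more OCA patients are lost.** The documents give no loss rates by arm, so these are assumptions. Placebo loss stays at 10% (27 evaluable).

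- OCA loss 20%: 30 × 0.80 = 24 evaluable; power at 0.78 SD is 77.8%.
- OCA loss 30%: 30 × 0.70 = 21 evaluable; power at 0.78 SD is 74.7%.

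**4. Shift in MELD change.** Suppose that lost patients would have done worse than those kept by k SD. An arm's observed mean is then too favourable by (fraction lost) × k, and the bias in the difference is (OCA loss − placebo loss) × k.

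- Extra loss 10%, k = 0.5: 0.10 × 0.5 = 0.05 SD.
- Extra loss 10%, k = 1.0: 0.10 × 1.0 = 0.10 SD.
- Extra loss 20%, k = 0.5: 0.20 × 0.5 = 0.10 SD.
- Extra loss 20%, k = 1.0: 0.20 × 1.0 = 0.20 SD.

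With no true effect, the two-sided type I error of that comparison is about 5.4% at the mildest setting and 10.3% at the most severe. Equal loss by the same mechanism in both arms gives no bias when there is no effect. All of this describes an unadjusted observed-case comparison, not the planned mixed model.

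**5. SAE proportion.** One missed first event in an arm of 30 moves the proportion by 1/30 = 3.3 percentage points.

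**The case against.** The case against has real force, and much of it stands.

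- **Nothing is ordered.** Section 5.7 asks for an assessment. The third reason in 4.3.2 concerns refusal, not missed tablets, and the investigator should discuss a discontinuation in advance with the study physician where possible. Section 4.3.3 offers a route for staying in off drug. This stands: the wording permits removal and does not require it.
- **A reader might infer that the text contradicts intention to treat.** It does not. No section excludes anyone from the analysis set; early exit creates missing data. The random-intercept model in 10.1 uses the Day 14 and Day 28 values, and not imputing is compatible with intention to treat if data are missing at random. Bias in MELD change needs loss that depends on unobserved outcomes.
- **A reader might infer that removed patients' outcomes are never collected, or that their SAEs no longer count.** Section 6.2.9 asks for exit assessments, which include MELD, and an SAE before removal already meets the endpoint. Only a later first SAE can be missed.
- **A reader might infer that heavier loss on OCA is to be expected.** The evidence is mixed. Section 1.2.2.1 also reports that in 747-202 pruritus was not elevated at 10 mg. Both trials were in PBC with 3-month double-blind phases, and the double-blind discontinuation percentages given for pruritus are for 50 mg.
- **The size is assumed.** Nothing in the documents links pruritus or missed tablets to worse MELD, and the exit route tied directly to MELD is the one where 4.3.1 keeps patients in.

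What remains is that continued follow-up is possible under the text but not guaranteed. The mixed model also gives no protection to the chi-square comparison of SAEs.

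**Conclusion.** The concern holds as a gap in the follow-up rules. Sections 5.7 and 4.3.2 allow a randomised patient to leave the trial for reasons that treatment may affect, and 4.3.1, 4.3.3 and 6.2.9 narrow the gap without closing it. The intention-to-treat comparison can be weakened; the documents do not show that it is contradicted or that bias will occur.

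Differential loss is plausible, not established. Under the assumed extra OCA loss of 10–20% and a deficit of 0.5–1 SD, the shift of 0.05–0.20 SD is smaller than the planned standard error of 0.27 SD, and power falls by about 2 to 6 points from 80.3%. The effect on SAEs depends on how many first events fall after exit, which the documents cannot tell us. The case for amending rests on the low cost and on the fact that lost follow-up cannot be repaired later.

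**What to change.** - **5.7:** make the final sentence govern continuation of study medication instead of eligibility for the trial.
- **4.3.2:** separate stopping study medication from leaving the trial, leaving the clinical decision to stop drug as it is. State that patients who stop drug for an adverse event or non-compliance are still invited to all Table 1 visits, with MELD and SAE collection to Day 180 unless consent is withdrawn. Where a trial procedure caused the adverse event, that procedure may be omitted while other follow-up continues.
- **6.2.9 and 4.3.3:** reconcile them, so that patients who stop drug but stay in follow the scheduled visits, and the exit assessment applies only to those leaving the trial.
- **10.5:** a missing-data sensitivity analysis would be a useful complement, since some loss will remain.

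The visits and tests are already planned in Table 1. The cost is an amendment needing IRB approval at each site, plus effort spent following poorly compliant patients, whose data may still be incomplete.
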